## 9.7. Safety Analysis

The safety analyses will be performed using the safety population, defined as all subjects who are randomized and receive at least one dose of investigational product. Safety will be assessed by clinical review of all relevant parameters including treatment emergent adverse events (TEAEs), laboratory tests, and vital signs; no inferential testing for statistical significance will be performed. Data from safety assessments will be summarized descriptively for the Placebo-controlled Phase (Weeks 0 to 16) and the Apremilast Exposure Period when subjects receive apremilast treatment. For safety analyses in the Placebo-controlled Phase, baseline will be relative to the first dose date following randomization at Week 0. For safety analyses in Apremilast Exposure Period, baseline will be relative to the first apremilast dose date at Week 0 for subjects initially randomized to apremilast or Week 16 for subjects initially randomized to placebo and switched to apremilast in the Apremilast Extension Phase (Weeks 16 to 32).

Adverse events will be classified using the Medical Dictionary for Drug Regulatory Activities (MedDRA) classification system. All TEAEs will be summarized by system organ class, preferred term, severity and relationship to investigational product. TEAEs leading to death or to discontinuation from treatment and SAEs will be summarized and listed separately.

Data from other safety assessments will be summarized descriptively. Shift tables for laboratory parameters showing the number of subjects with values low, normal, and high compare to the normal reference ranges pretreatment versus post treatment will be provided.

To account for the different exposure to the investigational product, AEs or marked laboratory abnormalities will also be summarized using the exposure adjusted incidence rate, in addition to the simple incidence rates.

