4.2.8.1. Treatment-emergent Adverse Event

An AE is a treatment-emergent AE (TEAE) if the AE start date is

- On or after the date of the first dose of investigational product (IP) and no later than 28 days after the last dose of IP for subjects who have completed study treatment or have discontinued early by the time of database cut, or
- On or after the date of the first dose of IP for subjects who are ongoing with study treatment at the time of database cut.

If the treatment-emergent status of an AE is unclear due to a missing/incomplete start date, it will always be considered treatment-emergent, unless shown otherwise by data. Date imputation rules for missing AE start dates are described in Appendix A1.

Adverse event started more than 28 days after the last dose of IP will not be considered as a treatment-emergent AE.

4.2.8.2. Treatment-emergent Adverse Event Leading to Drug Withdrawal, Drug Interruption, or Death, and Drug-related Treatment-emergent Adverse Event

A TEAE leading to drug withdrawal is a TEAE for which the investigator indicates that the action taken with respect to IP is withdrawn permanently. A TEAE leading to drug interruption is a TEAE for which the investigator indicates that the action taken with respect to IP is interrupted. A TEAE leading to death is a TEAE for which the outcome is fatal. Relationship to IP is based on the investigator's causality judgment; that is, a drug-related AE is an AE indicated by the investigator to have a suspected relationship to IP.

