5.1.1. Analysis Phases

Per protocol specification, data summary and analysis will be provided for the following phases.

• Placebo-controlled Phase – Weeks 0 to 16

This phase starts on the day of randomization (Week 0/Visit 2), and stops on either: (1) the day the first IP for the next phase is dispensed at Week 16/Visit 7; or (2) the day of the discontinuation visit if the subject discontinued prior to or at Week 16/Visit 7; or (3) the last known study day if the subject is lost to follow-up prior to Week 16/Visit 7 during the phase.

For safety analysis in subjects who continued treatment in Apremilast Extension Phase (Weeks 16 to 32), the phase stopped one day prior to the first dose date in Apremilast Extension Phase.

For the analysis of measured (ie, visit-based) safety data (ie, labs, vital signs, and ECG), this period is exclusive of the date of the first dose of IP and inclusive of the date of the first Week 16 dose of Apremilast.

At the time of the Week 16 analysis, if the date of the first Week 16 dose of Apremilast (derived from the Study Drug Exposure eCRF which may not be entered by sites until the next visit after Week 16) is not yet available for subjects with Apremilast dispensed at Week 16 and on or before the (possibly derived) date of the last dose of IP as of the time of analysis (ie, no evidence that the subject has discontinued without receiving at least one dose of Apremilast after Week 16), the date of Apremilast dispensing at Week 16 will replace the date of the first Week 16 dose of Apremilast in the above definition for these subjects.

• Apremilast Extension Phase – Weeks 16 to 32

This phase starts on the day after the first IP is dispensed for the phase at Week 16/Visit 7, and stops on either: (1) the day of Week 32/Visit 10; or (2) the day of the discontinuation visit if the subject discontinued prior to or at Week 32/Visit 10; or (3) the last known study day if the subject is lost to follow-up prior to Week 32/Visit 10 during the phase.

For safety analysis, the phase started at the first dose date in the phase and ended at the last dose date + 1.

• Observational Follow-up Phase – 4 weeks

Subjects who complete the study or discontinue the study early, will be followed up for 28 days after the last dose of IP.

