5.1.2. Apremilast-exposure Period for Safety Analysis

Apremilast-exposure Period will be used for safety analyses.

• Apremilast-exposure Period:

This period starts on the date of either: (1) the first dose of IP following randomization (Week 0/Visit 2) for subjects who are treated with apremilast from Week 0; or (2) the first dose of IP from the IP dispensed at Week16/Visit 7 for subjects who were originally treated with placebo and are treated with apremilast at Week 16.

This period stops on either: (1) data cut-off date; or (2) the end of the study.

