9.1.3. Apremilast-exposure Period

Treatment duration for Apremilast-exposure Period (Section 5.1) is calculated from the date of the first dose of apremilast, which is the date of the first dose of apremilast after randomization at Week 0/Visit 2 or switched to apremilast at Week 16/Visit 7, to the last apremilast dose date for subjects who discontinue in the first 32 weeks or who complete the study at Week 32/Visit 10. Imputation rule for partially or completely missing last dose date is specified in Appendix A1.1.4.

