11. SAFETY ANALYSIS

Safety will be assessed via descriptive statistics. Unless otherwise specified, all safety analyses described in this section will be performed for both the Placebo-controlled Phase and the Apremilast-exposure Period. The safety analyses for the Placebo-controlled Phase will be based on the safety population and presented by treatment group (placebo arm or apremilast arm), and the safety analyses for the Apremilast-exposure Period will be based on the apremilast subjects as treated population and presented by treatment group (Placebo/30 mg BID, 30 mg BID as Initiated and 30 mg BID as Treated).

For the analyses of AEs and lab marked abnormalities, the following endpoints will also be summarized:

- Subject incidence: Subject incidence (i.e., percentage [%] used in a frequency summary) is defined as the number of subjects with the specific event divided by the number of subjects included in the analysis. Subjects with multiple occurrences of the specific event in the specific analysis period will be counted only once in the numerator.
- Exposure-adjusted incidence rate (EAIR) per 100 subject-years: The EAIR per 100 subject-years is defined as 100 times the number of subjects with the specific event divided by the total exposure time (in years) among subjects included in the analysis. Subjects with multiple occurrences of the specific event in the specific analysis period will be counted only once in the numerator. The exposure time for a subject without the specific event is the treatment duration, whereas the exposure time for a subject with the specific event is the treatment duration up to the start date (inclusive) of the first occurrence of the specific event. The total exposure time in years is calculated by dividing the sum of exposure time in days over all subjects included in the analysis by 365.25. The EAIR per 100 subject-years is interpreted as the expected number of subjects with at least one occurrence of the specific event per 100 subject-years of exposure to the IP.

AEs and lab marked abnormalities will be summarized by subject incidence and EAIR for the Placebo-controlled Phase (Weeks 0 to 16) and for the Apremilast-exposure Period. In addition, selected summaries for the Apremilast Extension Phase (Weeks 16 to 32) and the Observational Follow-up Phase (4 weeks) may be presented if deemed necessary.

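### SAP 11: for the Apremilast-exposure Period, the AE exposure-adjusted rate can count first events up to 28 days after last dose over person-time that stops at last dose

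*SAP*

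**What the plan says.** **Events counted.** SAP 4.2.8.1 makes an AE treatment-emergent if it starts on or after first dose and "no later than 28 days after the last dose of IP", for subjects who have finished or stopped treatment. On the Apremilast-exposure Period, SAP 5.1.2 says: "This period stops on either: (1) data cut-off date; or (2) the end of the study". The four follow-up weeks therefore lie inside the period. Protocol 6.3.1 and 10.1 collect AEs over those 28 days.

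**Person-time.** SAP 11 says: "The exposure time for a subject without the specific event is the treatment duration". For a subject with the event, it is treatment duration up to the start of the first occurrence. SAP 9.1.3 runs treatment duration in this period from first apremilast dose "to the last apremilast dose date for subjects who discontinue in the first 32 weeks" or who complete at Week 32.

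**Stated meaning.** SAP 11 reads the EAIR as the expected number of subjects with at least one event "per 100 subject-years of exposure to the IP".

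**Related wording.**
- Protocol 9.7 refers to "the Apremilast Exposure Period when subjects receive apremilast treatment".
- For the Extension Phase, SAP 5.1.1 says: "For safety analysis, the phase started at the first dose date in the phase and ended at the last dose date + 1".
- SAP 11 says that selected Follow-up Phase summaries "may be presented if deemed necessary", whereas SAP 5.1.3 commits to summaries for subjects who enter follow-up.
- SAP 11.1.2 gives a denominator rule for the exposure-interval tables of the Placebo-controlled Phase. It then lists the Apremilast-exposure intervals, the last being more than 32 weeks, without repeating the rule.

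**The concern.** A rate per unit of exposure needs events and time at risk from the same window. Here the event window can extend 28 days beyond the time window, and no section limits the EAIR numerator to on-drug events or adds follow-up time to the denominator. Protocol 9.7 says the rate is there to account for different exposure to the investigational product. Off-drug events over on-drug time work against that purpose.

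The mismatch need not fall equally on the columns shown together. Subjects in Placebo/30 mg BID have up to 16 weeks on drug and those in 30 mg BID as Initiated up to 32, so the same four extra weeks weigh about twice as much in the former for events with a roughly constant rate. In the interval tables, a post-dose event in a Week 32 completer could fall in the row for more than 32 weeks, where there is almost no person-time.

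**Working it through.** The documents state no AE rate, EAIR or exposure total, so there is no plan figure to reproduce.

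**1. Direction.** Let E_on and E_off be the numbers of subjects whose first event starts on drug or in the 28 days after last dose, and T the person-time to first event or last dose.

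- Rate as written: (E_on + E_off)/T
- On-treatment rate: E_on/T

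The first exceeds the second whenever E_off > 0, and they are equal when E_off = 0. Illustration with assumed counts: 287 subjects at 224 days and 287 at 112 days, no dropout, give 287 × 336/365.25 = 264.0 subject-years. With 20 on-drug and 3 off-drug first events, the rate as written is 23/264.0 = 8.71 per 100 subject-years against 20/264.0 = 7.58 on treatment (+15%).

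**2. Does the wording for subjects with the event rescue it?** Suppose exposure for an off-drug event ran to the event date. That adds at most 28 days per such event. The rate still exceeds the on-treatment rate unless the latter is above 36,525/28 ≈ 1,304 per 100 subject-years. Subjects without the event stop at last dose under either reading.

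**3. Size in completers.** Let f be the off-drug to on-drug event rate ratio (assumed; not in the documents). For a rare event with a constant on-drug rate and W weeks on drug, E_on is proportional to W and E_off to 4f, so the factor is 1 + 4f/W.

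| f | W = 32 (as Initiated) | W = 16 (Placebo/30 mg) |
|---|---|---|
| 0 | 0% | 0% |
| 0.5 | 2/32 = 6.3% | 2/16 = 12.5% |
| 1 | 4/32 = 12.5% | 4/16 = 25% |

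The excess shrinks for common events. At an on-drug rate of 200 per 100 subject-years and f = 1, the rates as written are 211.8 (+5.9%) and 233.6 (+16.8%).

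**4. Dropout.** Assume 20% uniform dropout in each 16-week phase (20% is the planning figure in Protocol 9.3; applying it to both phases is an assumption).

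- As Initiated: 287 = 57 (mean 8 weeks) + 46 (mean 24) + 184 (32). Person-weeks: 456 + 1,104 + 5,888 = 7,448.
- Placebo/30 mg: 230 = 46 (mean 8 weeks) + 184 (16). Person-weeks: 368 + 2,944 = 3,312.

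Excess at f = 1 is 4 × (subjects followed off drug)/person-weeks:

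| Followed for 28 days | As Initiated | Placebo/30 mg |
|---|---|---|
| Everyone | 1,148/7,448 = 15.4% | 920/3,312 = 27.8% |
| Completers only | 736/7,448 = 9.9% | 736/3,312 = 22.2% |

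The no-dropout values are 12.5% and 25%, so dropout can move the excess either way.

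**5. Early-onset events.** Assume 10% of subjects have the event in the first 2 weeks, then 0.1% per week. At f = 1 the excess is 2.8% (32 weeks) and 3.2% (16 weeks), an artificial between-group ratio of 1.004. With the same inputs, a fully matched EAIR is 23.2 against 40.7 per 100 subject-years, a 1.76-fold difference due to exposure length alone.

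**6. Placebo-controlled Phase.** For subjects who continue, phase and treatment duration both end the day before the first extension dose (SAP 5.1.1, 9.1.1). For those who stop, the phase ends at the discontinuation visit, planned within 4 days of last intake (Protocol 11.1). At f = 1 and 20% dropout the excess is 0.2 × (4/7)/(0.8 × 16 + 0.2 × 8) = 0.114/14.4 = 0.8%.

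**The case against.** **The 28-day window is deliberate.** It is part of the SAP's definition of a treatment-emergent event, and cutting it from the EAIR gives one term two event counts. That is a real cost, and a reason to allow the alternative of adding follow-up time to the denominator. It does not make the present ratio a rate per subject-year of exposure.

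**The Protocol is not contradicted.** A reader might infer that SAP and Protocol disagree over which AEs count. They do not: the clause in Protocol 9.7 is descriptive and gives no end date, and Protocol Table 2 sets the AE timeframe to the end of follow-up. What remains is wording to align.

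**The interval rule probably carries over.** The Apremilast-exposure intervals follow directly after the rule in SAP 11.1.2, so this is the natural reading. One confirming sentence suffices.

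**Off-drug events stay visible.** SAP 5.1.3 already promises Follow-up Phase summaries, and SAP 11.1.6 lists all serious AEs. That objection largely stands; only the permissive wording in SAP 11 needs to be brought into line.

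**Nothing is decided on these rates.** This stands and limits the weight of the point.

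**Conclusion.** The mismatch is in the text and no other section repairs it, but its impact is minor. Its size rests on f, on constant rates and on how many subjects are followed after last dose. It is nil if no first events occur off drug. Safety is descriptive, overall subject incidence does not use this person-time, the randomized comparison moves by about 0.8% at most under the assumptions above, and the error overstates risk. Laboratory EAIRs are largely unaffected, because the Table of Events schedules no laboratory draw at the follow-up visit.

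Three stronger readings are tempting and not supported:
- **Dropout enlarges the excess.** This holds only if those who drop out contribute the full 28 days. Protocol Table 3 says subjects will be asked to enter follow-up, and loss to follow-up and withdrawal are listed reasons for stopping.
- **Off-drug rates exceed on-drug rates because psoriasis flares after stopping.** Protocol 6.5 describes flare as unusual worsening during treatment and does not record gradual worsening as an AE. The documents give no value of f.
- **The mismatch drives differences between the two apremilast columns.** For early-onset events, unequal exposure length does far more, and matching the windows will not change that.

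**What to change.** In SAP 5.1.2 and 11, make the EAIR windows match for the Apremilast-exposure Period, by one of two routes:
- count in the EAIR numerator only first events starting on or before the last dose date, which fits the meaning SAP 11 gives the rate; or
- keep the 28-day TEAEs, add follow-up time at risk to the denominator, and relabel the rate.

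Then:
- align the period wording in SAP 5.1.2 with Protocol 9.7;
- in SAP 11.1.2, apply the same window to the Apremilast-exposure interval tables and confirm that the interval denominator rule carries over;
- keep post-dose TEAEs in overall subject incidence;
- align SAP 11 with SAP 5.1.3, so that Follow-up Phase AEs are a firm output;
- footnote the tables with both windows.

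The cost is a few definitions, a programming change and a firm Follow-up Phase AE table, with no new data. Under the on-treatment route, EAIR and subject incidence will show slightly different event counts for the same term, and EAIRs will be slightly lower.

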11.1. Adverse Events

AEs will be coded according to the MedDRA version 21.0 or higher. Unless otherwise specified, AEs will be summarized by SOC and PT, with SOCs presented in the standard international order and PTs within SOCs will be presented in descending order of subject incidence.

11.1.1. Overall Summary of TEAEs

An overall summary of the following TEAE categories will be provided for the Placebocontrolled Phase (Weeks 0 to 16) for subjects with:

- Any TEAE
- Any drug-related TEAE
- Any severe TEAE
- Any serious TEAE
- Any serious drug-related TEAE
- Any TEAE leading to drug interruption
- Any TEAE leading to drug withdrawal
- Any TEAE leading to death

In addition, for Apremilast Exposure Period overall summary of TEAEs will also be provided.

11.1.2. All TEAEs

All TEAEs will be summarized by SOC and PT as well as by PT only (in descending order of subject incidence for the Placebo-controlled Phase (Weeks 0 to 16) and the Apremilast-exposure Period.

New events of all TEAEs by exposure interval (≤ 1 , > 1 to ≤ 4 , > 4 to ≤ 8 , > 8 to ≤ 12 and > 12 Weeks) will be summarized for the Placebo-controlled Phase. Each subject is counted once for either subject incidence or EAIR for each applicable specific TEAE in each exposure interval where an event started. The denominator of a subject incidence is the number of subjects with the exposure time reaching the lower bound of the particular exposure interval, and the denominator of an EAIR is the sum of the exposure time during the exposure interval (up to the start date [inclusive] of the first occurrence of the specific event for each subject reporting the event in the interval) among the same number of subjects as in the denominator of the corresponding subject incidence.

In addition, new events of all TEAEs by exposure interval (≤ 1 , > 1 to ≤ 8 , > 8 to ≤ 16 , > 16 to ≤ 24 , > 24 to ≤ 32 , > 32 Weeks) will be summarized for the Apremilast-exposure Period.

All TEAEs will be summarized by age category ($< 65, \ge 65$ years), sex, race (white vs. non-white), baseline sPGA categories (sPGA =2; sPGA =3) and, if deemed necessary, by prior/concomitant psoriasis medication usage or baseline disease characteristics.

11.1.3. Common TEAEs

TEAEs with subject incidence \geq 5% (or another cut-off if justified) in any treatment group will be summarized by SOC and PT as well as by PT only in descending order of subject incidence.

11.1.4. Drug-related TEAEs

Drug-related TEAEs will be summarized and new events of drug-related TEAEs by exposure interval (see Section 11.1.2) will be summarized.

11.1.5. TEAEs by Maximum Severity

All TEAEs will be summarized by maximum severity (mild, moderate, severe, and, if needed, missing; EAIR will not be provided for this summary). If a subject reports multiple occurrences of a specific event within a specific analysis phase or period, the subject will be counted only once by the maximum severity. If the severity is missing for one or more of the occurrences, the maximum severity of the remaining occurrences will be used. If the severity is missing for all of the occurrences, the subject will be counted only once in the "missing" category of severity.

TEAE by maximum severity will be summarized for the Placebo-controlled Phase (Weeks 0 to 16) and Apremilast-exposure Period.

In addition, severe TEAE will be summarized for the Placebo-controlled Phase (Weeks 0 to 16), the Apremilast Extension Phase (Weeks 16 to 32), and Apremilast-exposure Period.

11.1.6. Serious TEAEs

Serious TEAEs and serious drug-related TEAEs will be summarized.

New events of serious TEAEs and serious drug-related TEAEs by exposure interval will be summarized for Placebo-controlled Phase (Weeks 0 to 16).

Serious TEAEs will be summarized by age category ($< 65, \ge 65$ years), sex and race.

A subject data listing of all serious AEs (both TEAEs and non-TEAEs) will be provided.

11.1.7. TEAEs Leading to Drug Interruption and Drug Withdrawal

TEAEs leading to drug interruption and TEAEs leading to drug withdrawal will be summarized.

TEAEs leading to drug withdrawal will also be summarized by age category ($< 65, \ge 65$ years), sex and race.

A subject data listing of TEAEs leading to drug withdrawal will be provided.

11.1.8. **Deaths**

TEAEs leading to death will be summarized. A subject data listing of all deaths will be provided.

11.1.9. Onset/Duration of TEAEs for Selected PT

Onset and duration (Days) of diarrhea, nausea, headache, vomiting and tension headache will be summarized for the Placebo-controlled Phase (Weeks 0 to 16) and Apremilast-exposure Period.

11.1.10. Adverse Events of Special Interest

Summary tables and listings may be provided for the AESIs if deemed necessary.

11.2. Vital Signs and Weight

The endpoints for vital signs and weight include:

- Observed value and change from baseline over time in vital signs (temperature, pulse, and blood pressure)
- Shifts from baseline to post-baseline time points and to the worst post-baseline value in terms of normal/abnormal in pulse and blood pressure (normal ranges are defined as: 60-100 beats/minute for pulse, 90-140 mmHg for systolic blood pressure, and 60-90 mmHg for diastolic blood pressure)
- Observed value, change and percent change from baseline over time in weight

Summary statistics of observed values and changes from baseline in vital signs (including weight, for which percent change from baseline will also be summarized) will be provided over time. Frequency summaries (shift tables) of shifts from baseline to post-baseline time points and to the worst post-baseline value in terms of normal/abnormal will be provided for pulse and blood pressure.

Frequency summaries of change and percent change in weight from baseline to the end of the period will be provided by baseline BMI category ($<25, \ge 25$ to $<30, \ge 30$ to $<35, \ge 35$ to <40, and ≥ 40 kg/m²) and by baseline weight category ($<70, \ge 70$ to $<85, \ge 85$ to <100, and ≥ 100 kg). The categories of weight change (kg) and percent change (%) are $<-20, \ge -20$ to $<-10, \ge -10$ to $<-5, \ge -5$ to <0, 0, >0 to $\le 5, >5$ to $\le 10, >10$ to ≤ 20 , and >20. The end-of-period or end-of-phase value is the last post-baseline value in the analysis period or phase (excluding the value obtained at the follow-up visit, if applicable) up to 28 days after the last dose of IP in the study.

A subject data listing of all vital signs and weight data will be provided.

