4.2.8.3. Vital Signs and Weight

Vital signs and weight endpoints include:

- Observed value and change from baseline over time in vital signs (temperature, pulse, and blood pressure)
- Observed value, change and percent change from baseline over time in weight
- Shifts from baseline to post-baseline timepoints and to the worst post-baseline value in terms of normal/abnormal in pulse and blood pressure (normal ranges are defined as: 60-100 beats/minute for pulse, 90-140 mmHg for systolic blood pressure, and 60-90 mmHg for diastolic blood pressure)

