4.2.8.4. Clinical Laboratory Evaluations

Laboratory evaluations include:

- Observed value and change from baseline over time in hematology and serum chemistry parameters
- Laboratory marked abnormalities (see Appendix A2)
- Shifts from baseline to post-baseline time points and to the worst post-baseline value in terms of normal/abnormal (low or high) in hematology and serum chemistry parameters

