Descriptive statistics will be provided for vital signs, weight, height and BMI, laboratory values (continuous measurements) by treatment and visit, including the end of treatment visits. The baseline value, value at the time point, and change from baseline will be summarized for subjects who have values at baseline and at the time point.

Shift tables, that is, tables that summarize the baseline categories (normal, abnormal) versus the category at the end of the respective periods or versus the worst post-baseline category, include subjects who have values at baseline and at least one post-baseline value. Similarly, in frequency summaries of shifts from baseline at scheduled study weeks per protocol, only subjects who have values at baseline and at the time point will be included.

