11.3. Clinical Laboratory Evaluations

The endpoints for clinical laboratory evaluations include:

- Laboratory marked abnormalities (see Appendix A2)
- Observed value and change from baseline over time in the following laboratory parameters including but not limited to
 - Complete blood count: red blood cell [RBC] count, hemoglobin, hematocrit, white blood cell [WBC] count and differential, absolute WBC counts, platelet count
 - Serum chemistry: total protein, albumin, calcium, phosphorous, glucose, total cholesterol [TC], triglycerides, high-density lipoprotein [HDL], high-density lipoprotein cholesterol [HDL-C], low-density lipoprotein cholesterol [LDL-C], uric

acid, total bilirubin, alkaline phosphatase, aspartate aminotransferase [AST; serum glutamic-oxaloacetic transaminase, SGOT], alanine aminotransferase [ALT; serum glutamic pyruvic transaminase, SGPT], sodium, potassium, chloride, bicarbonate [carbon dioxide, CO₂], blood urea nitrogen, creatinine, lactate dehydrogenase [LDH], and magnesium

- Dipstick urinalysis: specific gravity, pH, glucose, ketones, protein, blood, bilirubin, leukocyte esterase, nitrite, and urobilinogen
- Shifts from baseline to post-baseline time points and to the worst post-baseline value in terms of normal/abnormal (low or high) in the above hematology and serum chemistry parameters

Summary statistics of observed values and changes from baseline in laboratory parameters will be provided over time. Frequency summaries (shift tables) of shifts from baseline to post-baseline time points and to the worst post-baseline value in terms of normal/abnormal will be provided.

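### Pulse and blood-pressure shift tables use one abnormal class on two-sided ranges, so low and high values are pooled; the laboratory shifts keep them apart

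*SAP*

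**What the plan says.** The vital-sign shift is defined in SAP 4.2.8.3 "in terms of normal/abnormal in pulse and blood pressure", and SAP 11.2 repeats this for the endpoint: "Shifts from baseline to post-baseline time points and to the worst post-baseline value in terms of normal/abnormal in pulse and blood pressure". The output sentence in SAP 11.2 again says shift tables "in terms of normal/abnormal will be provided for pulse and blood pressure". The normal ranges are "60-100 beats/minute for pulse, 90-140 mmHg for systolic blood pressure, and 60-90 mmHg for diastolic blood pressure", so each parameter can be abnormal in two directions. The general definition in SAP 11 also names two classes only: "Shift tables, that is, tables that summarize the baseline categories (normal, abnormal) versus the category at the end of the respective periods".

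The laboratory shifts are worded differently. SAP 4.2.8.4 gives them "in terms of normal/abnormal (low or high) in hematology and serum chemistry parameters", and SAP 11.3 says the same: "in terms of normal/abnormal (low or high) in the above hematology and serum chemistry parameters". Protocol 9.7 asks for low, normal and high categories, but only for laboratory parameters.

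SAP 11.2 also plans observed values and changes from baseline over time for pulse and blood pressure, and a listing of all vital-sign data. SAP 11 presents the continuous summaries by treatment and visit. SAP Appendix A3 includes minimum and maximum among the summary statistics.

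**The concern.** A two-class table on a two-sided range cannot say which limit was crossed. A count of normal-to-abnormal shifts is then the sum of two different findings, and an excess in the rarer one is diluted by the commoner one.

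This matters somewhat more for pulse and blood pressure than it would for laboratory data. Laboratory parameters also have marked-abnormality criteria (SAP Appendix A2), which point in a stated direction and are reported as incidence and exposure-adjusted rate. Weight has its own signed change categories in SAP 11.2. For pulse and blood pressure the shift tables are the only planned output that counts subjects by category. Protocol 9.7 makes the safety assessment descriptive, without inferential testing, so what the tables show is what a reader compares between arms.

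**Working it through.** The plan gives no figure to reproduce. The check has three parts.

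**1. What the two-class table merges.** With low, normal and high there are 3 × 3 = 9 cells; with normal and abnormal there are 2 × 2 = 4.

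| Planned cell | Cells merged into it |
|---|---|
| normal to normal | 1 |
| normal to abnormal | 2 (normal-low, normal-high) |
| abnormal to normal | 2 (low-normal, high-normal) |
| abnormal to abnormal | 4 (low-low, low-high, high-low, high-high) |

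Example with the SAP's own limits: systolic 150 at baseline and 85 later is abnormal both times, so no shift is shown. Pulse 55 then 110 gives the same result.

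**2. How far one tail can dilute the other (pulse).** The documents give no pulse distribution, so the means and SDs below are assumptions, with pulse taken as normal. Low = Φ((60 − mean)/SD); high = 1 − Φ((100 − mean)/SD); low share = low/(low + high). The last column triples the high tail and leaves the low tail unchanged, as an illustration.

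| Assumed mean (SD) | Low | High | Pooled abnormal | Low share | Pooled if the high tail triples |
|---|---|---|---|---|---|
| 73 (11) | 11.9% | 0.7% | 12.6% | 94% | 14.0% |
| 76 (11) | 7.3% | 1.5% | 8.7% | 83% | 11.7% |
| 80 (12) | 4.8% | 4.8% | 9.6% | 50% | 19.1% |

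In the first row a threefold rise in fast pulse raises the pooled row by a factor of 14.0/12.6 = 1.11. In the third row the factor is 19.1/9.6 = 2.0. Dilution is strong in one case and mild in the other.

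**3. How often a complete systolic reversal would be hidden.** Assume systolic mean 128, SD 15, with the same distribution at baseline and at one later visit. P(above 140) = 1 − Φ(12/15) = 21.2%; P(below 90) = Φ(−38/15) = 0.56%. With independent readings, the expected number per arm of 287 is 0.2119 × 0.00565 × 287 = 0.34. Under a bivariate normal it is 0.07 at correlation 0.3 and 0.009 at correlation 0.5.

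**The case against.** **Direction is reported elsewhere.** This stands. The by-arm continuous summaries give signed changes with minimum and maximum, and the listing gives every value. A clinically important event reported as an adverse event would appear by preferred term (SAP 11.1.2). None of these gives a count by direction and arm, however. A mean moves little when few subjects change: 4 more subjects of 287 rising by 30 beats/minute shift the arm mean by 4 × 30/287 = 0.4. A minimum or maximum shows one subject.

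**The wording may be shorthand.** This stands in part. The closing laboratory sentence in SAP 11.3 also says only normal/abnormal, and the two-class definition in SAP 11 covers laboratory shifts that are meant to be directional. But for laboratory data the split is written out first; for vital signs it never is. The table shells are not among the documents. If three classes are intended, the edit only records that.

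**The undefined worst value.** With two classes it does no harm, because any value outside the range counts as abnormal. A rule is needed once direction is restored.

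**Stronger readings to avoid.** A reader might infer that the roughly one subject in five above 140 mmHg under the assumed systolic distribution measures what the table hides. It does not: a hidden reversal needs a fall of more than 50 mmHg, and part 3 of the check puts that well under one subject per arm per visit. Repeated visits or a drug effect would raise it. A reader might also link the protocol's dose titration for gastrointestinal effects to a pattern of low pressure with fast pulse. The documents name no such risk, and tables made one parameter at a time would not show the joint pattern even with three classes.

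**Conclusion.** The concern holds, with modest impact. As written, the pulse and blood-pressure shift tables pool opposite abnormalities, and no section of either document restores direction to them. The pooling follows from the SAP's ranges alone. The size of the dilution rests on assumed normal distributions: low values make up between 50% and 94% of abnormal pulse over the three sets tried. Hidden reversals should be rare.

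It would be too strong to say that direction is lost from the report, or that these are the only categorical vital-sign outputs. The loss is confined to the shift tables, and weight has categories of its own. No endpoint, test or efficacy conclusion depends on the point. It is still worth correcting, because the SAP already applies the more informative rule to laboratory data.

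**What to change.** In SAP 4.2.8.3, 11 and 11.2, define the shift classes for pulse, systolic and diastolic pressure as low, normal and high relative to the ranges already given. Replace the single shift to the worst value with two: one to the lowest and one to the highest post-baseline value.

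Each table grows from 4 to 9 cells, and there is one more worst-value table per parameter. No new data are needed and no other analysis changes. SAP 2 says the plan is to be finalized before the Week 16 database is unblinded; the edit should be made by then, so that the choice of direction does not follow sight of the data.
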